#### *Sample size calculation*

The sample size calculation is based upon the primary aim, which is to examine the association between PIS on lung ultrasound and raised LVEDP on cardiac ultrasound. Available data on women with late onset preeclampsia and severe features suggest that the incidences of PIS and raised LVEDP are 23/95 (24%; 95% CI: 16-34%), and 20/80 (25%; 95% CI: 16-36%) respectively. In that population, the proportion of women with raised LVEDP was 12% in patients without PIS, and 55% in those who had PIS. A sample size of 60 (45 LVEDP negative and 15 LVEDP positive) will be required to detect a significant difference in incidence of PIS between the 2 groups (52% [expected PIS positive rate in women with raised LVEDP] versus 15% [expected PIS positive rate in women with normal LVEDP]) with a power of 80% and significance level of 0.05. To allow for the possibility of poor image acquisition during positive pressure ventilation, 70 patients will be recruited.

[figure not shown]

Figure 1: Comparison of normal lung in Panel A versus B-line pattern in Panel B.

[figure not shown]

Figure 2 (Image from Ref.): Measurement of the optic nerve sheath diameter in the coronal axis. The view is obtained in a sharply demarcated circle, measured in its widest diameter (A). If edema is seen, the measurement is taken at the outer edge (B, outer calipers).

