#### *F) Statistical analysis*

Data will be presented as mean and standard deviation for continuous variables, and frequency and percentage for categorical variables. For the a priori defined ultrasound outcomes of PIS, diastolic dysfunction, and increased ONSD, the prevalence and 95% confidence intervals will be calculated. In addition, the prevalence and 95% confidence intervals of systolic dysfunction and of raised LVEDP will be calculated.

Patients with and without ultrasound abnormalities will be compared with respect to admission systolic and diastolic blood pressures, clinical features of disease severity, and mean BNP levels using 2-sample t-test and the Chi-square test, for continuous and categorical variables respectively. The associations between PIS, increased ONSD or diastolic dysfunction with clinical severity features (=high arterial blood pressures, presence of pulmonary edema, headaches or visual disturbances, raised liver or renal laboratory parameters tests, and low platelet count), serum albumin level, BNP level, and between cardiac and pulmonary ultrasound abnormalities, will be explored using the 2-sample t-test and the Chi-square test, for categorical and continuous variables respectively. To adjust for multiple comparisons, including primary and secondary outcomes, a Benjamini-Hochberg correction will be applied using a 10% false discovery rate. Assuming that the p-value will result from 32 direct comparisons made in the study, the significance level will be adjusted to  $p < 0.025$ .

In order to determine pre- and post-test probabilities of PIS to predict elevated LVEDP, and of BNP at a level above 200 pg/ml to predict systolic dysfunction, diastolic dysfunction, elevated LVEDP, and the presence of PIS, sensitivity, specificity, positive and negative predictive value will be calculated.

Intra- and inter-observer agreement will be evaluated using the Bland and Altman method, after reviewing 10% of lung- (using total B-line score), cardiac- (using left ventricular internal diameter in diastole (LVEDD), and optic nerve (using the left optic nerve sheath

diameter) parameters; results will be expressed both graphically and quantitatively as mean difference (bias) and 95% limits of agreement.

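### The primary comparison is sized at a significance level of 0.05 but is to be judged at p < 0.025, where 60 evaluable women give about 72–73% power, not 80%

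*Combined protocol and SAP*

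**What the plan says.** Under *Sample size calculation*, the primary aim is the association between PIS on lung ultrasound and raised LVEDP on echocardiography. The plan states: "A sample size of 60 (45 LVEDP negative and 15 LVEDP positive) will be required", to detect PIS rates of 52% with raised LVEDP and 15% with normal LVEDP, "with a power of 80% and significance level of 0.05". A margin is then added for unusable images: "To allow for the possibility of poor image acquisition during positive pressure ventilation, 70 patients will be recruited".

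Under *F) Statistical analysis*, the plan states: "To adjust for multiple comparisons, including primary and secondary outcomes, a Benjamini-Hochberg correction will be applied", at a 10% false discovery rate. It continues: "Assuming that the p-value will result from 32 direct comparisons made in the study, the significance level will be adjusted to" p < 0.025.

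No text exempts the primary comparison from the correction, and the sample size section does not mention the adjusted level.

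**The concern.** There are two inconsistencies.

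- **Between the sections.** The sample size rests on 0.05, while the analysis section applies 0.025 and names primary outcomes as covered. The stated 80% is then not the power of the test as it will be judged.
- **Within the analysis section.** Benjamini-Hochberg is a step-up procedure whose cut-off depends on the rank of each p-value among all the tests. A fixed p < 0.025 is a different rule, yet the two are presented as one.

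The verdict on the primary aim could depend on which statement is followed. A primary p-value between 0.025 and 0.05 meets the level used for sizing and fails the fixed level in the analysis section. Under the step-up rule it could go either way, depending on the other 31 tests. If this is not settled beforehand, the choice could be made after the result is seen.

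**Working it through.** **Inputs** (all from *Sample size calculation* unless noted)

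- PIS rate with raised LVEDP, p1 = 0.52; with normal LVEDP, p2 = 0.15
- n1 = 15, n2 = 45
- Sizing level 0.05; sidedness is not stated and is taken as two-sided
- Analysis level 0.025, 32 comparisons, 10% false discovery rate (from *F) Statistical analysis*)

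**Formula.** Two proportions, pooled variance under the null, normal approximation, no continuity correction:

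power = Φ{ [ |p1 − p2| − z(1−α/2) × SE0 ] / SE1 }

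- Pooled rate = (15 × 0.52 + 45 × 0.15) / 60 = 14.55 / 60 = 0.2425
- SE0 = √[0.2425 × 0.7575 × (1/15 + 1/45)] = 0.1278
- SE1 = √[0.52 × 0.48/15 + 0.15 × 0.85/45] = 0.1395

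**Step 1: reproduce the plan.** At α = 0.05, z = 1.960: (0.37 − 1.960 × 0.1278) / 0.1395 = 0.857, so power is 80.4%. Solving for 80% power returns 15 + 45 = 60. One-sided 0.05 would give 87.4%, so the two-sided reading is the one that matches.

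**Step 2: apply the level in the analysis section.** At α = 0.025, z = 2.241: (0.37 − 2.241 × 0.1278) / 0.1395 = 0.599, so power is 72.5%. Exact enumeration of the uncorrected chi-square test gives 72.2%. Fisher's exact test gives 66.8% and the continuity-corrected chi-square 62.0%, so the figure is not pessimistic as to the choice of test.

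**Step 3: vary the number evaluable at p < 0.025, same 1:3 split.**

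| Evaluable | Power, normal approximation |
|---|---|
| 60 | 72.5% |
| 64 | 75.4% |
| 70 (no losses) | 79.1% |
| 72 (18 + 54) | 80.3% |

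With all 70 evaluable, exact chi-square power is 80.8% (17/53) to 81.4% (18/52). By the formula that reproduces the plan's 60, reaching 80% at 0.025 takes 72 evaluable women, more than will be recruited.

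**Step 4: compare the fixed level with Benjamini-Hochberg.** The cut-off at rank k is 0.10 × k / 32.

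| Rank k | Cut-off | Power of a single test at that cut-off (15/45) |
|---|---|---|
| 1 | 0.0031 | 47.8% |
| 8 | 0.025 | 72.5% |
| 16 | 0.05 | 80.4% |
| 32 | 0.10 | 87.4% |

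The last column is power at a fixed cut-off. Power under the step-up procedure depends on how many of the other comparisons are rejected, which the documents do not allow one to calculate. The table shows only that 0.025 is one value among 32.

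**Step 5: how often the choice matters.** By exact enumeration at the plan's rates, the chi-square p-value is below 0.05 with probability 83.0% and below 0.025 with probability 72.2%. The probability of landing between the two is 83.0 − 72.2 = 10.8%. For example, PIS in 7/15 versus 9/45 gives χ² = 60 × (7 × 36 − 9 × 8)² / (15 × 45 × 16 × 44) = 4.09, p = 0.043.

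**The case against.** The strongest reply has four parts.

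- **The 0.05 is a sizing input, not a decision rule.** Only the analysis section says how results are judged. This is a fair reading and narrows the ambiguity over the decision to fixed 0.025 versus step-up. But on that reading the 80% is simply misstated, because it was computed for a level that will not be used.
- **The planning rates may be conservative.** The plan reports from earlier data that "the proportion of women with raised LVEDP was 12% in patients without PIS, and 55% in those who had PIS". With PIS at 24%, raised LVEDP has overall probability 0.24 × 0.55 + 0.76 × 0.12 = 0.2232. PIS rates are then 0.132/0.2232 = 59% with raised LVEDP and 0.108/0.7768 = 14% with normal LVEDP. At 15/45 these give about 93% power at 0.05 and 88% at 0.025. This is a real mitigation. It assumes one common denominator, although the plan cites 95 women for PIS and 80 for LVEDP, and it is not the basis on which the plan claims 80%. The odds ratios differ (about 6.1 for 52%/15%, 9.0 for 55%/12%), so the planning rates are not a simple transposition of the earlier data. Their origin is missing detail and carries no weight in the conclusion.
- **The split is not fixed.** LVEDP status is observed, and the plan's interval for raised LVEDP is 16–36%. At p < 0.025 with 60 evaluable, power is about 62–63% for 10/50 and 78–80% for 20/40. This variation is wider than the loss of about 8 points from the change of level, so 72–73% is conditional on 15/45. It does not remove the mismatch.
- **Seventy women will be recruited.** The extra ten are reserved for poor images. Without any losses, power at 0.025 comes back to about 79–81%.

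Reading 0.025 as one-sided would restore 80.4%, but the plan introduces it as an adjustment for multiple comparisons.

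**Conclusion.** The concern holds; the plan is wrong as written. The 60-patient calculation is correct for two-sided 0.05, but that is not the level set for the primary comparison. At the stated p < 0.025, power is about 72–73%, given rates of 52% and 15%, a 15/45 split, 60 evaluable women and a two-sided test without continuity correction. The loss shrinks to about a point or vanishes if none of the 70 is lost, and disappears if the true rates are nearer 59% and 14%. Separately, and whatever the rates, the fixed 0.025 and Benjamini-Hochberg at 10% are different rules, and the plan does not say which governs. This should be fixed before analysis. It does not threaten the study design.

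**What to change.** Choose one rule for the primary comparison before the data are analysed, and state it identically in both sections, including that the test is two-sided.

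- **Option (a).** Test the single PIS-by-raised-LVEDP comparison once at two-sided 0.05, outside the multiplicity family. Apply step-up Benjamini-Hochberg at a 10% false discovery rate to the other comparisons. The existing sample size calculation then stands. This loosens the criterion now written for the primary outcome, so it should be a dated amendment made before results are known.
- **Option (b).** Keep 0.025 for the primary comparison and restate power as about 72–73% with 60 evaluable, and about 79% if all 70 are evaluable.

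Under either option, replace the fixed 0.025 for the remaining tests with the step-up rule, or keep the fixed level and drop the Benjamini-Hochberg name. A sentence giving the source of the 52% and 15% would help the reader.

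Both options cost only wording and need no extra patients; (b) makes the stated power less favourable. Restoring 80% at 0.025 by enlarging the study would instead take 72 evaluable women, or 72 / (60/70) = 84 recruited at the plan's own evaluable fraction.

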### **III. Ethics considerations**

#### **A. Risks and benefits**

There is very little risk to subjects participating in this study. If possible, venous blood samples will be taken as part of routine sampling performed in patients diagnosed with eclampsia. If not possible, a maximum of one venipuncture (1-2 ml) will be required in addition to routine blood sampling. In all cases, the blood samples will be taken and examinations performed as soon possible after admission, always allowing for prior initiation of normal obstetrics treatment protocols. Expected duration of blood sampling and ultrasound examinations is 30-45 minutes. In the event of demonstration of decreased systolic function (ejection fraction < 40%) and/or valvular heart disease, the obstetrics and anesthesia management team would be informed, since such findings could influence further management.

#### **B. Informed Consent**

Details of the consent process and data inclusion in the study are as follows:

1 Patients with eclampsia who are scheduled for induction of labour will have adequate cognition and the capacity for informed consent before the onset of labour. Patients will be given the consent form and given sufficient time to read it and ask questions. The discussion will be presented in an open, non-intimidating and educational format, in the patient's preferred language. All attempts will be made to minimise any anxiety that our study procedure may provoke; we will continually communicate with the patient regarding what to expect and explain that the investigations are noninvasive.

2 Patients who are scheduled for urgent caesarean section for maternal and/or fetal indications, will not have the capacity for informed consent at this time. In these cases, we will only be able to explain the study to the patient after clinical improvement from the post-anaesthesia state, and/or clinical improvement of their condition. Should the patient receive spinal anaesthesia, or be extubated immediately post-general anaesthesia, consent will proceed as in 1, above, as soon as there is full recovery from anaesthesia, and the patient has capacity.

3 In patients who require postoperative ventilation and who are haemodynamically stable, in order to avoid the risk of futility (since the important pathophysiological changes could be missed by delaying the noninvasive ultrasound protocol), the research group asks for an initial waiver of consent. We respectfully request that the family will not be contacted at this point, in the interest of allaying their anxiety in a stressful situation. The researchers therefore request “delayed consent”, which can be given by the patient (following stabilisation or recovery), or next of kin, or a legal representative or proxy. If the patient refuses consent, the data will not be used.

4 In view of recent work showing that in South Africa teenage mothers are at highest risk of eclampsia (Nathan et al, Journal of Global Health 2018:8: 020401), we request that minors (patients under the age of 18 years) may also be recruited for these noninvasive ultrasound scans. In these circumstances, parental approval will be requested, together with assent by the patient. The same initial waiver is respectfully requested for a patient requiring mechanical ventilation, as in 3, above. “Delayed consent” would then involve requesting parental approval and the assent of the patient after recovery. Should it be impossible to make contact with the parents, the research group will contact the HREC for a decision in the individual case.

4 In the unusual event of a diagnosis of intracerebral haemorrhage or stroke, the patient will be excluded from the study. In the rare event of the demise of a patient for any reason other than intracerebral haemorrhage or stroke, the researchers request that the data be included and analysed, after discussion with the HREC, for the reasons below.

The justifications for the above consent process and data inclusion are the following: Exclusion of patients without the capacity for consent, including minors, would lead to a biased sample, and data which is not generalisable to the majority of women with eclampsia. The generation of biased and poorly generalisable data would not address the research question and would thus dishonour the contributions of the other included patients, and would be wasteful research in a resource-limited environment.

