**E) Ultrasound procedures**

An ultrasound examination (approximately 35-40 minutes in duration) will be performed, at which time a venous blood sample will be taken. In addition to venepuncture for measurement of BNP, an additional 2 x 5 ml samples (in vacutainer serum separation collection tubes) will be taken for storage (-80°C) and subsequent batch serum measurement of sFlt-1, PIGF and Kisspeptin as surrogate biomarkers for placental dysfunction. The ultrasound examination will consist of evaluation of lung- and cardiac ultrasound, as well as optic nerve sheath diameter.

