#### C. Steps during the recruitment process to minimize potential coercion and anxiety

Patients will be assured that confidentiality will be guaranteed concerning any stored data, and that participation or non-participation in the study will not influence their quality of

care. Any patient anxiety will be allayed by sensitive discussion during the consent process; patients will be assured that the risks of ultrasound examination are minimal, and that the procedure is completely noninvasive. Patients will also be assured that they can withdraw from the study at any point.

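### The patient assurance, the request to enrol minors and the argument for the consent waiver speak only of noninvasive ultrasound, although research blood is taken at the same examination

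*Combined protocol and SAP*

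**What the plan says.** **Procedures.** II, E) Ultrasound procedures describes an examination "at which time a venous blood sample will be taken". The blood is for BNP, plus 2 x 5 ml for storage at -80°C and later measurement of sFlt-1, PlGF and kisspeptin. III.A Risks and benefits says research blood is combined with routine sampling where possible. Otherwise one venepuncture of 1-2 ml "will be required in addition to routine blood sampling". III.A applies early sampling to every case and makes no exception for ventilated women.

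**Consent text.** III.B Informed Consent has three relevant statements:
- Item 1 (women with capacity): staff are to "explain that the investigations are noninvasive". Item 2 refers back to item 1 for women who recover promptly after caesarean section.
- Item 3 (ventilated women): important changes "could be missed by delaying the noninvasive ultrasound protocol), the research group asks for an initial waiver of consent". Consent is then sought later, and a refusing patient's data are left out.
- First item numbered 4 (minors): they "may also be recruited for these noninvasive ultrasound scans". It adds: "The same initial waiver is respectfully requested for a patient requiring mechanical ventilation".

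III.C says patients will be assured that "the risks of ultrasound examination are minimal, and that the procedure is completely noninvasive".

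**The concern.** What patients and the ethics committee are told in III.B does not match what will be done. A venepuncture is not a noninvasive investigation, and frozen serum kept for later assays is not a scan. The groups affected include women who cannot consent at the time and girls under 18. For both, the request to the committee is the main safeguard, so it should name every research procedure. A woman with capacity is entitled to an accurate description before she agrees. At stake are the accuracy of the consent discussion, the clarity of what the committee is asked to approve, and the status of stored serum if a woman later refuses.

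**Working it through.** This is mainly a comparison of texts. The only arithmetic is a blood-volume sum and a check that the sample size does not depend on blood.

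**1. What is done.** Stored blood is 2 x 5 ml = 10 ml per woman, in addition to the BNP sample (II, E). A separate venepuncture is possible in any woman (III.A).

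**2. What III.B says, statement by statement.**
- *Item 1, assurance.* The subject is the investigations in general; blood is not excepted. If research blood is added to a routine draw, there is no extra puncture and the statement is merely incomplete. If a separate venepuncture is needed, it is inaccurate.
- *Minors.* The request names scans and nothing else. Neither II, E nor III.A exempts minors from sampling, so they will undergo a procedure that the request does not name.
- *Item 3, waiver.* The clause about delay gives ultrasound as the reason. The waiver that follows is not restricted to any procedure. Blood is neither named nor excluded.

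**3. Does the rest of Section III fill the gap?**
- III.A discloses sampling and the possible extra venepuncture. It does not mention freezing, storage or the placental biomarkers, and its 1-2 ml does not describe the 10 ml for storage (10/2 = 5 to 10/1 = 10 times as much).
- III.C refers to stored data, and III.D to coded data and ultrasound recordings. Neither covers serum.
- The refusal rule in item 3 covers data. II.C excludes women who withdraw or do not give retrospective consent, but does not say what is done with their samples.

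**4. Does it touch the primary analysis?** The plan's inputs are PIS rates of 52% and 15%, groups of 15 and 45, 80% power and significance level 0.05 (taken as two-sided, pooled variance, no continuity correction):
- Pooled rate = (15 x 0.52 + 45 x 0.15)/60 = 14.55/60 = 0.2425.
- Null SE = sqrt(0.2425 x 0.7575 x (1/15 + 1/45)) = 0.1278.
- Alternative SE = sqrt(0.52 x 0.48/15 + 0.15 x 0.85/45) = 0.1395.
- Power = Φ((0.37 - 1.96 x 0.1278)/0.1395) = Φ(0.86) = 80.4%.

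The stated 60 is reproduced, and 60/(1 - 1/7) = 70. No input involves BNP or stored serum, so correcting the consent text leaves both numbers as they are.

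**The case against.** A fair defence has four parts.

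*The committee is told about blood.* III.A comes directly before the consent text and discloses sampling in all women. The words granting the waiver are not limited to ultrasound; the clause before them gives a reason, not a scope. III.B also closes with a study-wide justification, that leaving out women without capacity, minors included, would bias the sample. That applies to blood results as much as to images. This stands. A reader might infer that sampling ventilated women exceeds the waiver requested; the documents show only that its scope is unclear.

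*The III.C assurance is accurate.* Its sentence concerns the ultrasound examination, and the procedure it calls noninvasive is that examination. This stands, and III.C is not criticised here.

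*The consent forms may mention blood.* They are not in the text reviewed, so this cannot be checked. It could soften the item 1 problem in practice. It would not repair the requests to the committee, which are made in III.B itself.

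*Postponing research venepuncture until consent is no simple remedy.* BNP is meant to be taken with the echocardiogram it is to predict, and postponement would separate the two. This stands, and postponement is not recommended here.

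None of this answers the item 1 assurance when an extra venepuncture is needed, the procedure missing from the minors request, or the silence on stored serum after refusal.

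**Conclusion.** The point holds as a mismatch between consent text and procedures. Two parts are firm: the item 1 assurance is inaccurate whenever a separate venepuncture is needed, and the request for minors omits blood sampling and storage. Two parts are gaps: it is unclear whether the waiver covers blood, and the plan does not say what happens to stored serum after refusal.

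A reader might go further and infer that BNP will be unusable in the sickest women, so that the BNP analyses lose a sizeable share of raised-LVEDP cases. The documents do not support this. Delayed consent from the patient or a representative could cover the samples, routine draws are the preferred source, and item 3 applies only to haemodynamically stable women. The number ventilated is not given. The 10 women added to the 60 are an allowance for poor images, not a count of ventilated women, and no rate of raised LVEDP in ventilated women is stated. No loss figure can be justified.

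The conclusion rests on reading the sections as they stand, without the consent forms. It is a participant-protection correction worth making before women are sampled under the waiver. It does not threaten the trial's results.

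**What to change.** Amend III.B in three places:
- **Item 1:** say that the ultrasound is noninvasive, that a blood sample will be taken (by separate venepuncture if it cannot be combined with a routine draw), and that part of it will be stored.
- **Item 3 and the item on minors:** name blood sampling and serum storage explicitly in the waiver request and in the request to recruit minors, so that the committee decides on them directly.
- **Refusal rule in item 3:** extend it from data to stored serum, and say what is done with the serum if delayed consent is refused.

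III.C needs no change on this point. The cost is an ethics amendment to the wording, with no added patients, procedures or analyses. The one risk is that the committee, asked directly, may set conditions on sampling under the waiver; the sponsor is better placed knowing that before samples are taken.
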